# **PARTNERS HUMAN RESEARCH COMMITTEE**

## **DETAILED PROTOCOL**

**Principal Investigator: [name]**

**Title: Vagus Nerve Stimulation: Integration of Behavior and Cardiac Modulation**

**September 5, 2017**

### **I. BACKGROUND AND SIGNIFICANCE**

Implantable VNS (iVNS) has been safely used to treat thousands of patients with depression. Eighty percent of the fibers in the vagus nerve are afferents that project to the periaqueductal grey (PAG), nucleus tractus solitarius, limbic system and thalamus. Secondarily, there are projections to the prefrontal cortex, inferior and superior parietal cortex and basal ganglia. Imaging studies in MDD patients have confirmed the broad reach of vagal afferents. In depressed patients, iVNS/fMRI interleaving activated bilateral orbitofrontal cortex, parieto-occipital cortex, hypothalamus, left amygdala and globus pallidus, areas implicated in the pathophysiology of MDD.

However, iVNS has side effects that limit its attractiveness as a treatment. The location of the stimulating electrode is within the vicinity of the recurrent laryngeal nerve, thus can cause hoarseness during stimulation, i.e. every 5 minutes. In addition, it is an invasive procedure with associated anesthesia and surgical risks. Transcutaneous VNS (tVNS) (placed in the ear) is an alternative that has been studied in healthy subjects. The auricular branch of the vagus nerve carries only vagal afferents unlike the vagal branch used in iVNS, which contains 20% efferents to the heart. Stimulating the auricular branch thus carries no risk of direct suppression of heart rate. tVNS is a non-invasive procedure that can be easily removed from the ear. Studies have shown that tVNS stimulates overlapping neural networks in healthy controls as iVNS in depressed patients, including hippocampus, amygdala, anterior cingulate, insula and thalamus. [name], collaborator, has demonstrated that tVNS decreases anxiety symptoms in women with chronic pain, a symptom highly comorbid in depression. Therefore, tVNS may be a lower risk and effective means of treating patients with MDD. Recently, a pilot study of tVNS was performed in depressed patients and demonstrated significant decreases in depressive symptoms compared to sham.

The circuits stimulated by VNS (i.e. mood circuitry) overlap with the circuits for autonomic nervous system (ANS) regulation. Heart rate variability (HRV) is an important measure of the health of ANS. HRV analysis indirectly estimates sympathetic and parasympathetic modulation of the heart. The peak in low-frequency spectral band (LF) is thought to be influenced by both parasympathetic and sympathetic activity. The peak in high-frequency band (HF) is influenced solely by parasympathetic (vagal) activity and the LF/HF ratio approximates the balance between sympathetic and parasympathetic modulation of the heart. Deficits in vagal tone have been found in patients with MDD as evidenced by decreased HF band. Vagal output from the hypothalamus projects to the heart and releases acetylcholine to slow heart rate. Vagal afferents provide feedback regulation of the heart through the nucleus tractus solitaires, which then projects to the heart. This feedback on heart rate can come from any of the vagal afferent branches. The auricular branch of the vagus nerve is an easily accessible vagus branch that can be directly stimulated. The dorsal medullary vagal system operates in tune with respiration, and therefore stimulation gated to exhalation/inhalation might have modulatory effects on vagal tone. The systematic

study of respiratory-gated tVNS in MDD patients may reveal whether in addition to regulating mood, it can regulate HRV.

Although deficits in vagal tone have been found in MDD, VNS has not yet been used in MDD patients to improve vagal tone. There have been reports of bradycardia and even asystole during implantation of iVNS. This may be due to direct stimulation of the vagal efferents of the target branch of the vagus. Although cardio-depressant effects have not been seen post operatively during active iVNS stimulation, modulation of vagal tone after iVNS has been reported. Complex studies of heart rate and the influences of vagal tone have not been performed in MDD with tVNS. Acupressure to the auricular branch of the vagus nerve restored sleep in post menopausal women. More importantly, the effect was only found in women who also had an increase in HF-HRV. If chronic tVNS normalizes HRV in MDD, it has the potential to have a significant impact on public health considering the high comorbidity between MDD and cardiovascular disease. Deficits in vagal tone have been associated with the comorbidity of MDD and CVD. Modulation of HRV chronically in MDD may thereby decrease risk for cardiac morbidity and mortality.

## **II. SPECIFIC AIMS**

Major Depressive Disorder (MDD) is a leading cause of morbidity and mortality worldwide. Abnormalities in vagal tone are more common in MDD, particularly loss of parasympathetic cardiac regulation, and increase the risk for cardiovascular disease (CVD). Vagal nerve stimulation (VNS) is an FDA approved treatment for MDD that modulates circuitry implicated in mood regulation. However it is unclear whether therapeutic benefit of VNS on mood, can also reduce cardiac morbidity and mortality. The circuits for autonomic cardiac regulation overlap with those for mood regulation, but modulation of ANS has not been directly associated with mood response. As a first step, we will identify whether VNS effects on mood circuitry in MDD are associated with modulation of vagal tone and mood.

In the proposed study in MDD patients, we will 1) identify the neural circuitry associated with tVNS, 2) identify its acute effects on heart rate variability, and 3) assess the impact of brain activity and ANS function on mood. We will control for factors known to impact vagal tone, in particular gonadal hormones in women. This is the first study to map the neurobiology of mood and vagal response to VNS using a less invasive form of VNS that may have a wider application.

**Specific Aim 1:** To determine the acute effects tVNS on cerebral blood flow in MDD patients.

Hypothesis 1: During real tVNS/fMRI interleaving, tVNS will deactivate amygdala, parahippocampal gyrus, hippocampus, posterior cingulate, and precuneus and will activate insula, thalamus and anterior cingulate.

Hypothesis 2: Brain activity deficits in stress response circuitry in MDD will be attenuated following 20 minutes of tVNS, in hypothalamus, amygdala, hippocampus, and anterior cingulate gyrus.

**Specific Aim 2:** To determine the acute effects of tVNS on vagal tone and mood in MDD patients.

Hypothesis 1: tVNS will increase high frequency R-R variability and decrease mood symptoms compared to baseline.

**Specific Aim 3:** To compare the effects of exhalation-gated tVNS with inhalation-gated tVNS on cerebral blood flow, vagal tone and mood regulation in MDD patients.

Hypothesis 1: Exhalation-gated tVNS will have a significant greater impact on regulation of cerebral blood flow, vagal tone and mood in MDD patients compared to inhalation-gated tVNS.

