## **V. STUDY PROCEDURES**

### **Study visits and parameters to be measured**

#### **Experimental Design Overview**

The fMRI scanning session will take approximately 90 minutes. There are 2 conditions, i.e. two scanning sessions (*note: 5 non-MDD test subjects have one scanning session only*). Both conditions will consist of one 30 minute tVNS session, one inhalation-gated the other exhalation-gated. During both

conditions, we will perform electrical stimulation to the ear, to stimulate the auricular branch of the vagus. Stimulation parameters will be identical.

[figure not shown]

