## **Scanning**

Subjects will be randomized as to the order of scan dates (inhalation-gated vs. exhalation-gated), which will be separated by at least one week. Scanning begins with the subject at full rest then they will undergo our mild visual stress paradigm for 18 minutes. Then the electrodes will be placed. The stimulation block will have a total duration of 30 minutes. The electrodes will be withdrawn at 20 minutes after and the mild visual stress task repeated. Patients will first undergo a mild stress task where they view pictures during fMRI scanning. Our fMRI stress paradigm has been described in detail previously and conducted in healthy subjects, MDD, and psychotic cases. Briefly, subjects view 3 stimulus blocks (6 images per block) for 30 seconds (1 image every 5 seconds) in the following order: fixation, neutral, and negative images (see definitions below). Subjects view this sequence 4 times during each of 3 runs for a total of 72 images (24 images per condition per run), and press a button each time a new image appears in order to ensure attention to the images, without adding cognitive load. Images were drawn from the International Affective Picture System (IAPS) according to affective valence and arousal (negative = unpleasant + high arousal, neutral = neutral + low arousal). Fixation images are based on Fourier transformations of each neutral image to create an image with the same physical properties of the original but without recognizable content. The stress task will be repeated after the tVNS portion of imaging. When the fMRI session is complete, subjects will be shown two blocks of negative and neutral images sampled from the set shown during imaging and will be asked to provide subjective ratings of arousal using the Self-Assessment Manikin (SAM).

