### **Magnetic resonance imaging data analysis**

Comparisons of interest in the fMRI analysis (BOLD signal changes during exposure to negative vs neutral images) will be tested using linear contrasts and results from the individual subject level will be submitted to a second-level factorial analysis with two factors: time of visual stress task (PRE- or POST-stimulation) and stimulation session (exhalation-gated or inhalation-gated). Significant interactions between these factors will be submitted to post-hoc analyses to determine directionality of the effect. Due to our a priori hypothesis of specific effects of tVNS on stress response circuitry, the analysis will be restricted to specific regions of interest (ROIs) using a small volume correction approach. A voxel-wise height threshold of  $p < 0.001$  (uncorrected for multiple comparisons), and a cluster correction with FWE  $p$ -value  $< 0.05$  will be applied. Mean beta weights within each significant cluster will be extracted for each participant using the REX toolbox and will be included in regression analyses in STATA (StataCorp, College Station TX) to investigate the link between variations in stress response circuitry activity and changes in depressive symptoms (BDI score difference: POST-PRE) after tVNS administration. Adjusted regression coefficients will be calculated after including baseline BDI scores and use of antidepressant medications in the models.

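### With active tVNS in both sessions and a fixed task–stimulation–task order, the PRE-to-POST changes in Aim 1 Hypothesis 2 and Aim 2 cannot be attributed to tVNS

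*Combined protocol and SAP*

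**What the plan says.** Section II (Specific Aims) states two hypotheses about what tVNS does over a session. Aim 1 Hypothesis 2: "Brain activity deficits in stress response circuitry in MDD will be attenuated following 20 minutes of tVNS". Aim 2 Hypothesis 1: "tVNS will increase high frequency R-R variability and decrease mood symptoms compared to baseline". Neither names a comparison condition other than the woman's own earlier measurement.

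The Experimental Design Overview in Section V describes the two sessions: "Both conditions will consist of one 30 minute tVNS session, one inhalation-gated the other exhalation-gated". It adds: "Stimulation parameters will be identical". The Scanning section fixes the order within a visit. It opens with "Scanning begins with the subject at full rest then they will undergo our mild visual stress paradigm for 18 minutes", stimulation follows, and then "The stress task will be repeated after the tVNS portion of imaging". On randomisation it says: "Subjects will be randomized as to the order of scan dates (inhalation-gated vs. exhalation-gated), which will be separated by at least one week". No sham session, no session without stimulation and no task–wait–task session is described. Section III gives the up to five non-MDD women the role of testing procedures in a single MRI session, so they are not a control group.

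Section VI crosses time (PRE, POST) with session (exhalation-gated, inhalation-gated) for mood, anxiety and the fMRI task response. HFn is taken during the negative pictures of the task. Nothing in Section VI limits what a PRE-to-POST change may be taken to show, and no adjustment for repetition or time in the scanner is named.

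**The concern.** A change from before to after an intervention supports a causal claim only if something shows what would have happened without the intervention. Here nothing does. At POST the woman has already done the task at least once that day, has spent longer in the scanner and, for mood, is answering the same questionnaires again after a procedure she knows to be active stimulation. Each of these can move BOLD response, HFn or mood ratings.

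Two of the stated hypotheses are at stake. If a PRE-to-POST difference appears, the aims invite the reader to call it an acute effect of tVNS on stress circuitry, vagal tone or mood in MDD. If none appears, drift in the opposite direction may have hidden a real effect. Neither result answers the question as worded.

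**Working it through.** The plan gives no figure for drift or for the size of a tVNS effect on mood or HFn, so there is nothing of its own to reproduce on this point. The check has two parts.

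**1. Can the design separate drift from tVNS?**

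Let h be the within-session drift, τ the effect of tVNS common to both gatings, and γ the extra effect of exhalation gating. Relative to each session's own PRE value, the mean of each cell is:

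| Cell | h | τ | γ |
|---|---|---|---|
| Inhalation, PRE | 0 | 0 | 0 |
| Inhalation, POST | 1 | 1 | 0 |
| Exhalation, PRE | 0 | 0 | 0 |
| Exhalation, POST | 1 | 1 | 1 |

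The h and τ columns are identical, so the matrix has rank 2 for 3 parameters.

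- Inhalation change = h + τ.
- Exhalation change = h + τ + γ.
- Time main effect = average of the two changes = h + τ + γ/2.
- Time-by-session interaction = difference of the two changes = γ.

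Only the sum h + τ is estimable. More participants or more covariates do not change that. The interaction is free of h if average drift is the same in both sessions, which the randomised order supports. It is also free of τ: if tVNS works equally well in both phases, the interaction is zero.

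Adding a session without active stimulation but with the same timing adds the rows (0, 0, 0) and (1, 0, 0). The rank becomes 3 of 3, and τ is estimable if drift is equal in both kinds of session.

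**2. How often would drift alone look like an effect?**

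Inputs: n = 20 (Section VI, Sample Size); τ = γ = 0; drift of d standard deviations of the PRE-to-POST change (assumed, hence a range); one two-sided 5% paired t test within one session. The test statistic is noncentral t with 19 degrees of freedom and noncentrality d√20. The critical value is 2.093.

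| d | d√20 | Chance of p < 0.05 |
|---|---|---|
| 0 | 0 | 5.0% |
| 0.2 | 0.894 | 13.6% |
| 0.3 | 1.342 | 24.7% |
| 0.5 | 2.236 | 56.5% |
| 0.8 | 3.578 | 92.4% |

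The planned mood ANOVA pools both sessions. The noncentrality of its time main effect is d√20 / √((1+ρ)/2), with ρ the correlation between a woman's two changes (also assumed). For ρ from 0.5 down to 0, the chance is about 17–22% at d = 0.2, 31–44% at 0.3, 69–85% at 0.5 and 97–100% at 0.8. In simulation (40,000 runs per setting) the interaction stayed at about 5% for every d.

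The imaging analysis uses a voxel threshold of p < 0.001 with cluster correction, so these tables do not describe it. A single t test at two-sided 0.001 would give about 0.6%, 1.7%, 9% and 42% at the same four drifts. That is not a model of cluster inference either.

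**The case against.** The strongest reply is that the text promises less than the concern assumes. Aim 2 says openly that its comparison is with baseline. For fMRI, Section VI sends significant interactions to post-hoc analysis and names no follow-up of a time main effect. The Cardiac Autonomic Analysis section spells out no PRE/POST test of HFn, and the behavioural section does not say which ANOVA term is confirmatory. The study calls itself a first step, and the randomised gating comparison in Aim 3 is intact. All of this is correct. It does not remove the problem: both hypotheses make tVNS the cause, and the only term that could test them is the PRE-to-POST change.

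Some stronger readings are tempting, and the documents do not support them:

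- *Habituation would produce exactly the predicted result.* Aim 1 Hypothesis 2 speaks of deficits being attenuated, which on its plain wording may mean activity rising towards normal. Habituation would then work against it. Repeated unpleasant pictures could also worsen mood at POST. The direction of bias is open.
- *There is no unstimulated period at all.* Stimulation alternates 30 seconds on and 30 seconds off during the runs, which gives Aim 1 Hypothesis 1 a valid within-run contrast. What is missing is a PRE-to-POST interval without stimulation.
- *The same pictures are shown every time.* The Scanning section says that the task is repeated, not whether the pictures are.
- *The interaction can stand in as the test of tVNS.* Both sessions are active, so it tests gating phase only.

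**Conclusion.** The concern holds for Aim 1 Hypothesis 2 and Aim 2 Hypothesis 1. Drift and tVNS are completely aliased in their PRE-to-POST changes, so the design cannot support the stated attribution. That conclusion needs no assumption about size.

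The size is illustrative only. With no tVNS effect and one within-session 5% test in 20 women, the chance of a significant change is 13.6% to 92.4% for assumed drifts of 0.2 to 0.8 SD. A reader might infer that these are the false-positive rates of the imaging analysis. They are not, because its thresholds are much stricter.

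A reader might also infer that the trial as a whole is uninterpretable. It is not. Aim 3's gating comparison is protected by the randomised order, and Aim 1 Hypothesis 1 does not depend on a PRE-to-POST change.

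**What to change.** In Section II and the analysis subsections of Section VI:

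1. Describe and report the PRE-to-POST results for Aim 1 Hypothesis 2 and Aim 2 as uncontrolled *change over the session*, not as an effect of tVNS. Apply the same wording to the regressions that relate brain measures to symptom change.
2. Name the time-by-session interaction as the randomised test, read as the effect of exhalation versus inhalation gating and not of tVNS itself.
3. Leave the 30-second on/off contrast of Aim 1 Hypothesis 1 unchanged.
4. Optionally, if the same pictures are used at PRE and POST, prepare matched, non-overlapping sets and counterbalance them over time and session. This removes item repetition only. Time in the scanner, general task habituation, repeat rating and expectation remain.

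Items 1 to 3 cost wording and a weaker claim for Aim 1 Hypothesis 2 and Aim 2. Item 4 costs some preparation and a small loss of comparability between sets, which counterbalancing averages out. No visit or participant is added. If the sponsor wants to keep the claim about tVNS itself, wording is not enough: a sham or no-stimulation session with matched timing would be needed, at the cost of a further scan for each woman.

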## **III. SUBJECT SELECTION**

About 25 female, right-handed subjects will take part in this research study at Brigham and Women's Hospital (BWH). (Up to) the first 5 subjects enrolled in the study will not have major depressive disorder (MDD). These non-MDD (test) subjects will do some of the study procedures so that we can make any changes before we enroll subjects with major depression. Following finalization of study procedures, up to 20 female subjects with MDD will be enrolled. Subjects with major depression will participate in 2 telephone screenings and/or a REDCap online questionnaire, an evaluation visit, two MRI testing sessions, and four follow-up evaluations. The non-MDD test subjects will only participate in the telephone screening and one MRI session.

## **Inclusion Criteria/Exclusion Criteria:**

### ***Inclusion Criteria***

Patients with MDD will be women between 25-40 years of age meeting DSM criteria of recurrent MDD as assessed by SCID. In addition, up to five non-MDD subjects will be enrolled to test all procedures prior to enrollment of MDD subjects. MDD patients with a comorbidity of PTSD will be considered for clinical applicability by our senior clinicians on a case by case basis.

### ***Exclusion Criteria***

- History of Axis I psychiatric diagnosis other than MDD or anxiety disorder - e.g., substance use disorder, psychotic disorder, or bipolar disorder.
- Current Suicidal Ideation with intent and/or plan or history of suicide attempt within the last year
- Use of psychotropic medications within four weeks prior to study with the exception of SSRI and SNRI class of antidepressant medication only
- Use of Tricyclic antidepressants (TCAs), Monoamine oxidase inhibitors (MAOIs), and Atypical agents
- History of cardiovascular disease
- History of neuroleptic use
- Past history of substance abuse or dependence within the past 12 months (excludes nicotine)
- Bleeding disorder or use of anticoagulants.
- Pregnancy
- Metallic implants or devices contraindicating magnetic resonance imaging.
- Use of beta blockers

### **Verbal Screening**

Women of childbearing age will be asked if they think they are pregnant and if they are trying to get pregnant. Upon self-report, if they are not sure whether they are pregnant, OR if they are trying to get pregnant, then they will not be allowed to participate in this study. Negative pregnancy test allows study entrance.

## **Source of subjects and recruitment methods**

Healthy adult female volunteers with MDD (and up to five test subject volunteers without MDD) will be recruited by poster, e-mail and website advertisements (see attached flier), phone call (with prior consent to contact), as well as from the outpatient psychiatry clinic and the registry Research Study Volunteer Program (RSVP for Health). The research assistant will first perform a phone interview with the subjects where an initial screening will take place to distinguish potential subjects from those not meeting eligibility criteria (as detailed above). If a potential subject responds to the REDCap online survey and meets eligibility criteria, the research assistant will contact the subject for further scheduling and to answer any questions. Efforts will be made to attain a mix of study participants in terms of racial/ethnic representation as determined by NIH guidelines. Children will not be included because of differences in

brain development with age. It would also be difficult for them to lie still throughout the scanning period. Patients will be recruited with the help of outpatient psychiatrists and colleagues.

## **IV. SUBJECT ENROLLMENT**

### **Method of enrollment**

When contacted by a potential volunteer, the research assistant will either first perform an initial screening interview via phone. This will be done to distinguish potential subjects from those not meeting eligibility criteria. During this initial interview, we will explain the purpose, procedures, and potential discomforts/risks of the study. If a potential subject responds to the REDCap online questionnaire and meets eligibility criteria, the research assistant will contact the subject to schedule her for a second phone screening and to answer any questions. If the subject is eligible by the initial phone screening or REDCap online questionnaire, a clinician Interviewer will have a second phone screening interview. This second phone screening interview will help determine if the subject is eligible for an in person evaluation. On the day of the evaluation, MDD subjects will again be explained the purpose, procedures, and potential discomforts/risks of the study. They will again undergo a deeper screening procedure and will be asked about their medical and psychiatric history and fill out a handedness questionnaire to assess that they are right handed (see attached forms/questionnaires). The evaluation is expected to take about 90 minutes. Only English speaking subjects will be enrolled as we do not have a Spanish speaking clinician to perform assessments. Non-MDD test subjects will only participate in the telephone screening and one MRI session, and thus will not participate in the fill screening appointment.

